ECG	Electrocardiogram
eCRF	Electronic case report form
EDC	Electronic data capture
EU	European Union
EudraCT	European Medicines Agency's Clinical Trials Database
FDA	Food and Drug Administration
GCP	Good Clinical Practice
HbA _{1c}	Glycated hemoglobin
ICH	International Conference on Harmonization
ID card	Identification card
IEC	Independent Ethics Committee
IM	Intramuscular(ly)
IMP	Investigational medicinal product
IRB	Institutional Review Board
IV	Intravenous(ly)
IWRS	Interactive Web Response System
MedDRA	Medical Dictionary for Regulatory Activities

CONFIDENTIAL

Sponsor:	Zealand Pharma A/S	Protocol Number:	ZP4207-16137
----------	--------------------	------------------	--------------

NPH	Neutral protamine Hagedorn
PD	Pharmacodynamics
PK	Pharmacokinetics
PP	Per protocol
SAE	Serious adverse event
SAP	Statistical analysis plan
SC	Subcutaneous(ly)
SUSAR	Serious unexpected suspected adverse reaction
T1DM	Type 1 diabetes mellitus
T2DM	Type 2 diabetes mellitus
TEAE	Treatment-emergent adverse event
tmax	Time to the maximum plasma concentration
ULN	Upper limit of the normal range
US	United States of America

CONFIDENTIAL

Sponsor:	Zealand Pharma A/S	Protocol Number:	ZP4207-16137
----------	--------------------	------------------	--------------

1 Introduction

This document presents the statistical analysis plan (SAP) for Zealand Pharma A/S, Protocol No. ZP4207-16137: A phase 3, randomized, double-blind, parallel trial to confirm the clinical efficacy and safety of dasiglucagon in the rescue treatment of hypoglycemia in subjects with type 1 diabetes mellitus (T1DM) compared to placebo and with reference to GlucaGen®.

This analysis plan is based on the final clinical trial protocol (Final, v3.0) dated 06OCT2017 and global protocol amendment 2 (Final, v1.0) dated 04APR2018. The SAP will be finalized and approved prior to the unblinding of the database.

The SAP provides the description of the statistical analysis for the final analyses.

2 Study Objectives

The objectives of this study are:

- Primary: To demonstrate superiority of dasiglucagon compared to placebo following a single subcutaneous 0.6 mg dose administered to subjects with type 1 diabetes mellitus with insulin-induced hypoglycemia.
- Secondary: To compare the glycemic response observed after dasiglucagon with that of GlucaGen.

2.1 Primary endpoints

The primary endpoint of this study is:

- Time to plasma glucose recovery. Plasma glucose recovery is defined as first increase in plasma glucose of ≥ 20 mg/dL (1.1 mmol/L) from baseline during the hypoglycemic clamp procedure without administration of rescue IV glucose.

2.2 Secondary endpoints

The secondary endpoints of this study are:

Key secondary endpoints

- Plasma glucose recovery within 30 minutes, within 20 minutes, within 15 minutes, and within 10 minutes after study drug injection without administration of rescue IV glucose.

CONFIDENTIAL

Sponsor:	Zealand Pharma A/S	Protocol Number:	ZP4207-16137
----------	--------------------	------------------	--------------

- Plasma glucose changes from baseline within 30 minutes, within 20 minutes, within 15 minutes, and within 10 minutes after study drug injection or at the time of rescue.

Other secondary endpoints

- Clinical efficacy (PD) endpoints:
 - Time to first plasma glucose concentration ≥ 70 mg/dL (3.9 mmol/L) without administration of rescue IV glucose.
 - Plasma glucose response as area under the curve (AUC) above baseline from time zero to 30 minutes, $AUC_{0-30\text{min}}$.
- Exposure (PK) endpoints:
 - Area under the drug concentration curve from time zero to 90 minutes, $AUC_{0-90\text{min}}$.
 - Maximum plasma drug concentration (C_{\max}).
 - Time to maximum plasma drug concentration (t_{\max}).
- Immunogenicity endpoint:
 - Occurrence of anti-drug antibodies

Exploratory endpoints

- Plasma glucose concentration ≥ 70 mg/dL (3.9 mmol/L) or increase of ≥ 20 mg/dL (1.1 mmol/L) within 30 minutes after study drug injection without administration of rescue IV glucose.
- Plasma insulin response as area under the curve above baseline from time zero to 60 minutes, $AUC_{0-60\text{ min}}$.

2.3 Safety endpoints

The safety endpoints of this study are summaries of the following:

- Adverse events, clinical laboratory assessments (biochemistry, hematology, urinalysis), vital signs, physical examination, electrocardiogram (ECG), and local tolerability.
- Administration of rescue infusion of IV glucose during the hypoglycemic clamp procedure.
- Time to first rescue infusion of IV glucose during the hypoglycemic clamp procedure.

CONFIDENTIAL

Sponsor:	Zealand Pharma A/S	Protocol Number:	ZP4207-16137
----------	--------------------	------------------	--------------

3 Study Design

3.1 Discussion of Study Design

This trial is a global, multicenter, randomized, parallel, double-blind, clinical trial confirming the efficacy and safety of dasiglucagon for insulin-induced hypoglycemia in subjects with T1DM. The subjects will be randomized 2:1:1 to receive a single fixed SC 0.6 mg dose of dasiglucagon, placebo, or a 1 mg dose of GlucaGen and followed for at least 28 days after receiving treatment. A total of 156 subjects with T1DM are expected to complete the treatment visit. This trial is planned to be conducted at 4 to 6 trial sites in the United States of America [US], Canada, and Europe.

3.2 Study Treatment

Subjects successfully completing screening and who fulfill entry eligibility and randomization criteria will be randomized to one of three treatment groups in a 2:1:1 ratio:

- Test treatment: Dasiglucagon, liquid formulation, 1 mg/mL, 0.6 mL delivered in a prefilled syringe.
- Placebo treatment: Placebo, liquid formulation, 0.6 mL delivered in a prefilled syringe.
- Recombinant glucagon hydrochloride, 1 mg for reconstitution (GlucaGen®, Novo Nordisk) in 1 mL sterile water.

Subjects will attend the study site at Trial Day -3 (Screening Visit 1, Day -30 to Day -1) for informed consent, Trial Day -1 to Day 1 for dosing (Dosing Visit 2, Day 1), and followed for at least 28 days after dosing in order to perform an adequate immunogenicity evaluation of treatment (Safety Follow-up Visit, Day 28 + 5).

3.3 Study Schedule

The schedule of procedures is provided in Protocol Table 3.

3.3.1 Visit 1 (screening, Day -30 to Day -3)

Visit 1 will take place between 3 and 30 days before Visit 2, Day -1 to Day 1 (dosing day).

Informed consent can be obtained prior to or at Visit 1, however it must in any case be obtained prior to any trial related procedures. During the screening visit, the following assessments will take place:

- Informed consent (obtain or check)
- Check of subject eligibility (inclusion/exclusion criteria)
- Demography

CONFIDENTIAL

Sponsor:	Zealand Pharma A/S	Protocol Number:	ZP4207-16137
----------	--------------------	------------------	--------------

- Body measurements
- Medical history, diabetes diagnosis, current diabetes treatment
- Concomitant illnesses
- Concomitant medications
- History of alcohol/drug abuse
- Physical examination
- Vital signs
- 12-lead ECG
- Adverse Events
- Biochemistry, hematology, coagulation, HbA_{1c}, C-peptide
- Serum pregnancy test (women of childbearing potential only)
- Urinalysis
- Urine drug screen
- Alcohol breath test

3.3.2 Visit 2 (dosing visit)

The subjects will attend the clinical center the day prior to dosing (Day -1) and should stay onsite overnight. Dosing will take place the following morning (Day 1).

On Day 1 and prior to the start of the insulin-induced hypoglycemic procedure, subject eligibility is rechecked (check of changes between the screening visit and Visit 2) and those subjects eligible to participate will be randomized to treatment with dasiglucagon, placebo, or GlucaGen.

The following assessments will also take place:

- Document all changes in concomitant medication (prior to the start of the insulin-induced hypoglycemic procedure)
- Check of withdrawal criteria (prior to the start of the insulin-induced hypoglycemic procedure)
- Check of dosing day exclusion criteria (prior to the start of the insulin-induced hypoglycemic procedure)
- Vital signs (prior to the start [within 30 minutes] of the insulin-induced hypoglycemic procedure, and at 30, 90 and 300 minutes after dosing). Blood pressure should be measured first in sitting and then in standing.
- 12-lead ECG (prior to the start [within 30 minutes] of the insulin-induced hypoglycemic procedure, and at 20, 35, 45, 60, and 300 minutes after dosing)
- Local tolerability (at 30, 120, and 300 minutes after dosing)
- AEs
- Biochemistry and hematology (prior to the start of the insulin-induced hypoglycemic procedure [within 30 minutes], and at 30 and 300 minutes after dosing)

CONFIDENTIAL

Sponsor:	Zealand Pharma A/S	Protocol Number:	ZP4207-16137
----------	--------------------	------------------	--------------

- Urine stick pregnancy test (women of childbearing potential only; prior to the start of the insulin-induced hypoglycemic procedure)
- Urinalysis (prior to the start of the insulin-induced hypoglycemic procedure [within 120 minutes])
- Urine drug screen (prior to the start of the insulin-induced hypoglycemic procedure)
- Alcohol breath test (prior to the start of the insulin-induced hypoglycemic procedure)
- Dasiglucagon/GlucaGen plasma concentrations:
 - Pre-dose, 15, 30, 35, 40, 50, 60, 90, and 120 minutes after dosing. The actual time of blood sampling for exposure should not deviate from the nominal time by more than ± 1 minute. Pre-dose is defined as within 2 minutes prior to dosing.
- Plasma glucose concentrations:
 - Pre-dose, 4, 6, 8, 10, 12, 15, 17, 20, 25, 30, 40, 50, 60, 75, and 90 minutes after dosing. The actual time for blood sampling for plasma glucose should not deviate from the nominal time by more than ± 30 seconds until the 20 minute collection time point and by more than ± 1 minute for the subsequent collection time points. Pre-dose is defined as within 2 minutes prior to dosing.
- Antibodies against dasiglucagon/GlucaGen (prior to the start of the insulin-induced hypoglycemic procedure).
- Plasma insulin concentrations:
 - Pre-dose, 30 and 60 minutes after dosing. The actual time of blood sampling for plasma insulin should not deviate from the nominal time by more than ± 1 minute. Pre-dose is defined as within 2 minutes prior to dosing.

3.3.3 Visit 3 (follow-up visit)

Visit 3 will take place on Day 28 + 5 days. The subject does not need to be fasting.

At Visit 3, the following assessments will take place:

- Document all changes in concomitant medication
- Physical examination
- Vital signs
- 12-lead ECG
- Local tolerability
- AEs
- Biochemistry, hematology
- Urine stick pregnancy test (women of childbearing potential only)
- Urinalysis
- Antibodies against dasiglucagon/GlucaGen.

CONFIDENTIAL

Sponsor:	Zealand Pharma A/S	Protocol Number:	ZP4207-16137
----------	--------------------	------------------	--------------

3.4 Concomitant Medication

A concomitant medication is any medication, other than the trial products and current diabetes treatment (including insulin glulisine [Apidra®] for diabetes therapy wash-out), which is taken during the trial, including screening and follow-up periods.

Details of any concomitant medication must be recorded at trial entry (i.e., at screening). Any changes in concomitant medication must be recorded at each visit as they occur. The information collected for each concomitant medication includes (at a minimum) trade name or generic name, indication, start date and stop date or continuation. A change in medication due to an AE must be recorded and reported according to Protocol Section 7.2.1 “Adverse Events”. If the change in medication influences the subject’s eligibility to continue in the trial, the sponsor and trial monitor must be informed.

3.5 Study Analysis Samples

For presentation of data and reporting of the statistical analyses, the following analysis samples will be used, depending on the context:

- Safety analysis set: All randomized subjects who received at least one dose of trial medication.
- Full analysis set: All randomized subjects who received at least one dose of trial medication.
- Per protocol (PP) set: All subjects of the Full analysis set for whom no relevant protocol deviations were documented. This sample will primarily be used for sensitivity analysis.

The analysis of the primary endpoint and secondary endpoints will be based on the Full analysis set. A secondary analysis of the primary endpoint will be based on the PP set. All safety analyses will be based upon the Safety analysis set, which is identical to the Full analysis set, but will be labelled as Safety analysis set.

The decision regarding whether a protocol deviation is relevant or not for the exclusion of subjects from the PP set will be made case-by-case in a blinded data review meeting prior to treatment unmasking and database lock (see Protocol Section 9.2.3 “Protocol Deviations”).

3.6 Withdrawn Subjects

Subjects withdrawn from the trial will be listed including the primary reason for withdrawal.

Any subject who withdraws after randomization will not be replaced. Withdrawn subjects will not be re-entered into the study.

CONFIDENTIAL

Sponsor:	Zealand Pharma A/S	Protocol Number:	ZP4207-16137
----------	--------------------	------------------	--------------

3.7 Randomization

Subjects who have given written informed consent and meet all inclusion and none of the exclusion criteria will be randomized to one of three treatment groups in a 2:1:1 ratio:

- Test treatment: Dasiglucagon, liquid formulation, 1 mg/mL, 0.6 mL delivered in a prefilled syringe.
- Placebo treatment: Placebo, liquid formulation, 0.6 mL delivered in a prefilled syringe.
- Reference treatment: Recombinant glucagon hydrochloride, 1 mg for reconstitution.

Randomization will be performed using a fixed-block randomization scheme. The randomization scheme will be generated prior to the initiation of the study by an independent statistician/programmer who will not be a member of the study team; all investigators will not be aware of the block size of the randomization scheme. Randomization will be stratified by treatment group and by injection site (abdomen, buttocks, or thigh) and controlled via the IWRS.

3.8 Blinding and Breaking the Blind

This is a double-blind trial. As the trial products are not identical in appearance, dasiglucagon and placebo being available as a liquid formulation and GlucaGen as a powder for reconstitution, unblinded trial personnel will be responsible for handling, preparing (according to the prescription from the IWRS), and administering the trial medication, as well as for keeping the records strictly confidential and accessible only to unblinded staff until after the database has been locked. To maintain double-blind conditions, all trial assessments at the trial center will be done by blinded trial personnel not involved in the administration of trial medications. However, exposure assessments and anti-drug antibody (ADA) assessments will be performed by unblinded personnel at the special laboratories, to ensure that dasiglucagon, placebo, or GlucaGen administration is matched with the applicable bioanalytical assay.

Treatment assignment will be kept strictly confidential and accessible only to authorized persons until after the time of unblinding. Codes with treatment assignment will, however, be readily available in the IWRS to the blinded personnel in case of an emergency.

The code for a particular subject may be broken in a medical emergency if knowing the identity of the treatment allocation would influence the treatment of the subject. The emergency code break can be performed using the IWRS. Whenever a code is broken, the person breaking the code must record the time, date and reason as well as his/her initials in the source documents. The breaking of blinded codes in case of medical emergency for one subject should not unblind the trial personnel to the treatment information of other subjects. The person performing the unblinding should inform as few people as possible about the result of the unblinding. All persons unblinded for a specific subject should be documented.

If the trial center needs to break the code, the medical monitor should, if at all possible, be contacted prior to breaking the code and the monitor must be notified within 24 hours after the code has been broken.

CONFIDENTIAL

Sponsor:	Zealand Pharma A/S	Protocol Number:	ZP4207-16137
----------	--------------------	------------------	--------------

The pharmacovigilance unit (safety contract research organization [CRO]; see Protocol Section 12.1 “List of Trial Personnel”) will be able to break the code in case of a serious unexpected suspected adverse reaction (SUSAR).

The central and specialty laboratories will be provided with a copy of the randomization list.

3.9 Sample Size

Due to requirements in the size of the safety database, the sample size is set to 78 subjects treated with dasiglucagon 0.6 mg. From phase 2, the median time to an increase of 20 mg/dL of the 0.6 mg dose was approximately 10 minutes. With a 2:1:1 randomization ratio for the three treatments, dasiglucagon 0.6 mg, placebo, and GlucaGen 1 mg, and assuming an exponential time-to-recovery distributions with median times of 10 and at least 20 minutes for dasiglucagon and placebo, respectively, a two-sided log-rank test will be able to detect a difference between dasiglucagon and placebo with 90% power with a follow-up time of 45 minutes at a 5% significance level with 78 subjects treated with dasiglucagon and 39 subjects with placebo. The median time-to-recovery for placebo is expected to be longer than 20 minutes, which means that the power will be greater than 90%.

4 Statistical Methodology

4.1 Planned Analyses

Before database lock and treatment unmasking, the statistical analysis plan (SAP) will be finalized, providing detailed methods for the analyses outlined below. Further analysis details may be added or refined in the SAP.

The analysis of the primary endpoint and secondary endpoints will be based on the Full analysis set. A secondary analysis of the primary endpoint will be based on the PP set. All safety analyses will be based upon the Safety analysis set.

The decision regarding whether a protocol deviation is relevant or not for the exclusion of subjects from the PP set will be made case-by-case in a blinded data review meeting prior to treatment unmasking and database lock (see Protocol Section 9.2.3 “Protocol Deviations”).

All data obtained in this trial and documented in the eCRFs will be listed and summarized with statistics or frequency tables as appropriate. In case of termination of the trial, all data collected up to that timepoint will be included in the analysis.

Raw data listings and summary tables will be generated using the software SAS[®] version 9.4 or higher.

Continuous variables will be summarized using means, standard deviations, medians, coefficients of variation, and minimum and maximum values. Other summaries (e.g. quartiles, 95% confidence intervals [CIs]) may be used as appropriate.

CONFIDENTIAL

Sponsor:	Zealand Pharma A/S	Protocol Number:	ZP4207-16137
----------	--------------------	------------------	--------------

Categorical efficacy and safety variables will be summarized by counts and by percentage of subjects in corresponding categories.

4.2 Interim Analysis

No interim analysis is planned for this study.

4.3 Disposition of Subjects

Subject disposition will be tabulated including the number of screened subjects, screening failures, subjects exposed to trial product, subjects completing the trial and subjects in each analysis set. A CONSORT diagram will be included to display the disposition of subjects.

Subjects withdrawn from the trial will be listed including the primary reason for withdrawal.

4.4 Baseline and Demographic Characteristics

Baseline assessments are defined as the last non-missing result prior to administration of the first dose of study medication. In cases where there are multiple such values, the non-missing value closest to the start of study treatment will be selected. If time is available for an assessment, it will be compared with dosing time of the first dose of study medication to define the baseline value.

Baseline and demographic data will be summarized using descriptive statistics. Baseline ADA-positive subjects will be calculated as a percentage of the total number of subjects whose baseline samples were tested for ADA.

Notes:

- Age will be calculated as (screening date – date of birth + 1)/365.25 and presented to 1 decimal place. Age will be rounded down to the nearest integer before analysis.
- BMI will be calculated as weight(kg)/height(m²)
- Medical history will be coded according to MedDRA, version 19.1.
- Active medical history is defined as histories marked as active at time of screening.
- Relevant medical histories are all medical histories recorded in the eCRF.
- Any duration [days] = end date – onset date + 1

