4.9.5 Vital signs

The following vital signs will be summarized for the Safety analysis set subjects:

- Systolic and diastolic blood pressure (mmHg)
- Pulse rate (beats/min)
- Body temperature (°C)

At the dosing visit, measurements will be taken prior to the start of the insulin-induced hypoglycemic procedure (within 30 minutes) and at 30, 90, and 300 minutes after dosing. The

CONFIDENTIAL

Sponsor:	Zealand Pharma A/S	Protocol Number:	ZP4207-16137
----------	--------------------	------------------	--------------

actual time of the assessment should not deviate from the nominal time by more than ± 10 minutes. In addition to the pre-specified assessments, blood pressure and pulse may be assessed at any time during the trial at the discretion of the investigator.

Vital signs data and changes from baseline in vital signs will be summarized by treatment group and time point where appropriate using standard descriptive statistics.

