5.3.7.3 Vital signs

- Table 14.3.3.1 Summary of Vital Signs Data – Actual and Change from Pre-Dose Measurement
- Table 14.3.3.2 Vital Signs – Overall Interpretation
- Table 14.3.3.3 Shifts Pre-Dose versus Post-Dose of Interpretation of Vital Signs Data

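### The general baseline rule lets a discretionary blood pressure or pulse reading, taken after the insulin procedure has started, replace the scheduled baseline, so change and shift tables can mix two reference states

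*SAP*

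**What the plan says.** Section 4.4 gives a single baseline definition for all assessments: "Baseline assessments are defined as the last non-missing result prior to administration of the first dose of study medication". With more than one candidate, "the non-missing value closest to the start of study treatment will be selected". The clock time that matters is the time of dosing: "If time is available for an assessment, it will be compared with dosing time of the first dose of study medication". The rule mentions neither the start of the insulin procedure nor any restriction to scheduled readings.

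For the dosing visit, section 3.3.2 schedules "Vital signs (prior to the start [within 30 minutes] of the insulin-induced hypoglycemic procedure, and at 30, 90 and 300 minutes after dosing". Section 4.9.5 repeats this schedule and adds that "blood pressure and pulse may be assessed at any time during the trial at the discretion of the investigator". It then states that "Vital signs data and changes from baseline in vital signs will be summarized by treatment group and time point", without a baseline definition specific to vital signs.

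The output list in section 5.3.7.3 titles Table 14.3.3.1 "Summary of Vital Signs Data – Actual and Change from Pre-Dose Measurement". Table 14.3.3.3 gives pre-dose to post-dose shifts in the interpretation of vital signs. Neither title says which pre-dose reading is meant.

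**The concern.** Treatment is given to subjects in whom hypoglycemia has been induced with insulin (section 2). Two different states therefore precede dosing: before insulin, and during the fall in glucose. The only scheduled Day 1 pre-dose vital signs belong to the first state. A discretionary reading taken after the procedure has started belongs to the second, and it is nearer to dosing, so section 4.4 selects it.

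Subjects without such a reading would have changes measured from the pre-insulin state, and subjects with one would have changes measured from the hypoglycemic state. Both kinds of change would enter the same column of the same table. Discretionary readings are usually prompted by something, so the subjects affected may not be typical of the rest. What is at stake is the meaning of the within-group changes and shifts in blood pressure and pulse.

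**Working it through.** The SAP has no figure of its own to reproduce here. The check sets the sections side by side, followed by an illustration on assumed inputs.

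**Applying the text**

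1. Candidates for baseline: any non-missing reading before dosing (4.4). Scheduled and unscheduled readings are not distinguished.
2. Scheduled candidate on Day 1: one set, within 30 minutes before the insulin procedure starts (3.3.2, 4.9.5).
3. Possible extra candidates: blood pressure and pulse at any time the investigator chooses (4.9.5). The interval from procedure start to dosing is not excluded. Body temperature is not named in that clause.
4. Selection: the candidate closest to dosing (4.4). Any recorded extra reading in that interval is closer than the scheduled one, so it is chosen.
5. Search for a limiting rule: sections 4.4, 4.9.4, 4.9.5 and 5.3.7.3 contain none. The definition of pre-dose as within 2 minutes of dosing (3.3.2, 4.5) is attached to blood samples, not to vital signs.

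The replacement therefore follows from the written rule and does not depend on a gap being filled in a particular way.

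**Illustration of size (pulse)**

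Let *f* be the share of subjects whose baseline is replaced and *d* the mean difference between the hypoglycemic-state and pre-insulin readings. The SAP gives neither. Change is post-dose minus baseline, so the group mean change moves by −*f* × *d*.

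- Smallest case assumed: 0.05 × 5 = 0.25 beats/min.
- Largest case assumed: 0.20 × 15 = 3.0 beats/min.

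If *d* is a constant 15 beats/min, unrelated to the rest of the change, and the SD of change is otherwise 10 beats/min (also assumed), the added variance is *f*(1 − *f*) × 15²:

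| *f* | Shift in mean | Added variance | SD of change | Increase |
|---|---|---|---|---|
| 5% | 0.05 × 15 = 0.75 | 0.0475 × 225 = 10.7 | √110.7 = 10.5 | 5% |
| 10% | 0.10 × 15 = 1.5 | 0.09 × 225 = 20.3 | √120.3 = 11.0 | 10% |
| 20% | 0.20 × 15 = 3.0 | 0.16 × 225 = 36.0 | √136.0 = 11.7 | 17% |

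For a single affected subject the difference is the whole of *d*. With an invented pulse of 70 before insulin, 90 in hypoglycemia and 60 after dosing, the tabulated change is 60 − 90 = −30 instead of 60 − 70 = −10. These figures show the mechanism and predict nothing about this trial. The constant-*d* assumption in particular is doubtful if readings are taken because something looked unusual.

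**The case against.** A last-value-before-dosing rule is ordinary practice, and it suits plasma glucose, whose baseline should lie just before dosing. For the rule to misfire on vital signs, a discretionary reading must be taken in the interval, be captured in the vital-signs data, and enter the baseline derivation. The SAP establishes none of these, and data-capture and programming specifications are not at hand. Actual values are tabulated beside the changes, and vital signs are listed in Listing 16.2.6, so a reader is not confined to the change column. All of this stands and limits the point. It does not remove it, because the SAP states a selection rule and that rule, as written, picks the later reading.

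Three stronger readings are tempting, and the document does not support them:

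- *The rule distorts the adverse events of special interest.* Hemodynamic changes are the events so designated, but section 4.9.1 defines them by post-dose clinical signs, measured vital signs and the investigator's judgment. They have their own table (14.3.1.4) and listing (16.2.4.2). The derived baseline can neither add nor remove one.
- *The rule creates false falls or hides real ones.* In the pulse example the fall from 90 to 60 across dosing did occur. Calling it false assumes that the pre-insulin state is the only valid reference, which the SAP nowhere says. The defect is that the reference differs between subjects.
- *The rule biases the comparison between arms.* The readings precede dosing, and section 3.8 assigns trial-center assessments to blinded staff, so affected subjects should be spread across arms by chance.

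**Conclusion.** The point holds as a minor one. Sections 4.4 and 4.9.5 together allow the blood pressure and pulse baseline to come from different physiological states in different subjects, and Tables 14.3.3.1 and 14.3.3.3 would combine them without notice.

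The number of subjects affected is unknown and may be zero. The conclusion assumes that a discretionary reading in the interval is recorded and reaches the baseline derivation, as the written rule would have it do. The vital-sign summaries are descriptive, with no test attached. The primary, key secondary and other efficacy endpoints do not use this baseline. The assumed range of 0.25 to 3.0 beats/min for mean pulse change has no source in the SAP and should not be cited as an expected effect.

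**What to change.** In sections 4.4 and 4.9.5, define the blood pressure and pulse baseline as the scheduled assessment within 30 minutes before the insulin procedure starts. Allow an unscheduled reading to serve only if it also precedes the start of the procedure and the scheduled one is missing. List all other unscheduled pre-dose readings, and do not use them as baseline. Use the same term in Tables 14.3.3.1 and 14.3.3.3. Leave the general rule in place for plasma glucose.

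The cost is a sentence or two in the SAP and a filter in the program, with no change to trial procedures. There is one small downside: every change from baseline will then include any effect of the induced hypoglycemia as well as of treatment. A table footnote should say so.
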